## Abstract

**Background:** High-flow nasal cannula (HFNC) is a device that can reduce the work of breathing (WOB) and improve oxygenation by providing a flow that matches or exceeds patient's peak inspiratory flow during tidal breathing. Despite its widespread use, there remains a lack of consensus regarding the optimal flow settings. Two new HFNC devices that can provide information regarding patient's peak tidal inspiratory flow breath by breath are recently available, which might help guide set and titrate the flow settings. This study aims to investigate the effects of different flow settings on lung impedance in a cohort of healthy volunteers by using the two new HFNC devices.

**Methods:** This prospective, randomized crossover trial will enroll adult healthy volunteers. Initially, the subject's peak inspiratory flow will be measured using a mask connected with a respiratory monitor. Subsequently, the volunteers will undergo HFNC treatment at different flow settings while their peak inspiratory flow will be continuously monitored. The primary outcome of this study is the lung aeration with different flow settings. Secondary outcomes include the lung aeration with different devices, subject's comfort at different flow settings, and the correlation between the subject's peak inspiratory flow measured by HFNC and by a mask connected with a respiratory monitor.

**Results:** N/A

**Conclusion:** N/A

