## Introduction

High-flow nasal cannula (HFNC) is a widely used medical device. It can deliver flows up to 60-100 liter per minute (LPM) and maintain a consistent fraction of inspired oxygen once the set flow exceeds the patient's tidal inspiratory flow (PTIF). HFNC has demonstrated effectiveness in reducing the risk of intubation in patients with hypoxic respiratory failure, and can improve ventilation in patients with chronic obstructive pulmonary disease. These effects can be attributed to the many benefits offered by the device, including improving ventilation/prefusion matching, reducing the work of breathing, and washing out the dead space of the upper airway. Furthermore, when the flow exceeds the PTIF, a positive end-expiratory pressure (PEEP) effect is observed. This PEEP effect can be estimated by measuring the end-expiratory lung impedance (EELI), which is reported to be correlated with HFNC flows. Despite recommendations that the set flow should match or exceed the PTIF, continuous measurement of PTIF, especially during HFNC treatment, remains challenging, and there is no consensus on optimal flow settings. Therefore, a continuous PTIF monitoring could serve as an objective reference for practitioners when determining the initial flow and flow titration for different patients and under different conditions.

Two new HFNC devices, the *OmniOx HFT7500* (MEK, Paju-si, South Korea) and the *Airvo3* (Fisher & Paykel Healthcare Ltd, Auckland, New Zealand), could potentially provide the solution. The *HFT7500* can continuously measure PTIF during therapy, while *Airvo 3* provides a continuous waveform reading of the targeted flow to assess if it meets patient's demand. However, the accuracy and effectiveness of these devices remain unknown. Thus, in our study, we will measure the participants' PTIF via a mask prior to applying the HFNC and compare the flows with those displayed by the HFNC devices during treatment, particularly at different flow settings. We will also measure the lung aeration of different flows using the two devices. Our aim is to investigate the effects of different flows on the homogeneity of lung aeration. Our hypothesis is that as flow setting increases, lung aeration (EELI) will also increase.

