## Methods

**Study Design:** Randomized crossover trial

**Inclusion criteria:** Healthy volunteers between 21-65 years old

**Setting:** Rush University

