**Exclusion criteria:**

- 1- Chronic pulmonary diseases, including COPD, interstitial lung disease, cystic fibrosis, etc.
- 2- Uncontrolled asthma;
- 3- Pregnancy
- 4- Subjects who have cold/flu symptoms (sore throat, runny nose, fever, chills, coughing)
- 5- Nose abnormalities that can affect the functionality of the nasal prongs

**Sample size:** 26 subjects

This study is a single group comparison study designed to compare the change of EELI with different flow settings during HFNC treatment. In the study by Plotnikow et al that compared HFNC flows of 30 vs 50 L/min, they reported that mean changes of EELI from baseline were 1.12 (0.8, 2.01) at 30 L/min and 1.44 (1.05, 2.16) at 50 L/min. We use this result to calculate the sample size, with confidence level (1 -  $\alpha$ ) of 95% and power (1 -  $\beta$ ) of 80%, the sample size is calculated to be 26.

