**Study Procedure:**

- 1- Study will be advertised at Rush University through a poster in a public place
- 2- Interested participants can contact the study investigator ([name]) through email or phone call which will be provided in the advertisement

- 3- Interested participants will be assessed for eligibility. If eligible, the study investigator will explain the whole study procedure and the benefits/harms to them in a private room, questions will be answered. Next, participants will be given a minimum of 30 mins to consider participating in the study. Consent will be obtained.
- 4- At the beginning, an electronic impedance tomography belt will be placed around the torso of the subjects according to their chest size. The participants will rest in a bed with head elevated at 30 degree.
- 5- Baseline measurement over 5 minutes of respiratory rate, tidal volume and PTIF will be obtained using a respiratory monitor (NICO2, Respiration, Murrysville, PA, USA) through a mask. Then the subject will be coached to breathe normally with room air for 20 mins, at the end, they will be questioned about their comfort level using a visual numerical scale ranging between 0 (extreme discomfort) and 10 (very comfortable).
- 6- HFNC devices ([HFT700](#)[HFT750](#) and Airvo 3) will be applied, three different flows will be utilized at a random sequence: 20, 40, and 60 L/min. Each flow will be utilized for 20 mins. There is a 5 min break between flows. HFNC will be removed during the break.
- 7- Between flow settings, PTIF will be measured via the mask and respiratory monitor
- 8- PTIF (measured by the [HFT700](#)[HFT750](#)) or targeted flow waveform (using Airvo 3), EELI, and respiratory rate will be monitored continuously through the procedure, and comfort level will be assessed at the end of each flow setting
- 9- The whole procedure is expected to last 3-4 hours

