## **Data Analysis**

Kolmogorov-Smirnov will be used to test the normality of distribution for continuous variables. Based on the distribution of the variables, continuous variables (respiratory rate, PTIF and comfort level) will be reported as mean and standard deviation (SD) or median and Inter-Quartile Range (IQR). Friedman or Repeated Measures ANOVA analysis will be used to compare the differences of continuous variables between baseline and 3 flow settings with each HFNC device. Mann-Whitney or independent t test will be used to compare the differences of continuous variables between two devices. Spearman's Rho or Pearson Correlation statistical test will be used to assess the correlation between PTIF measured via mask (NICO2) with PTIF measured by the HFT7~~500~~ device. A *p*-value of < 0.05 will be considered statistically significant. Data analysis will be conducted with SPSS software (SPSS 26.0; Chicago, IL).

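### The two devices are compared with tests for separate groups, although the documents imply that every volunteer uses both devices

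*Combined protocol and SAP*

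**What the plan says.** The Data Analysis section handles the two factors differently. For flows it names Friedman or repeated-measures ANOVA, both within-subject methods, to "compare the differences of continuous variables between baseline and 3 flow settings with each HFNC device". The next sentence, on devices, reads "Mann-Whitney or independent t test will be used to compare the differences of continuous variables between two devices". It does not say whether devices are compared at each flow or over all three flows together.

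The Abstract describes a study "in a cohort of healthy volunteers by using the two new HFNC devices" and adds "Secondary outcomes include the lung aeration with different devices". The Outcomes section lists EELI, respiratory rate and comfort between devices as well. The Introduction says "We will also measure the lung aeration of different flows using the two devices". Methods gives the design as "Randomized crossover trial", and the sample size paragraph states "This study is a single group comparison study designed to compare the change of EELI with different flow settings during HFNC treatment". Step 6 of the Study Procedure names both devices and continues "Airvo 3) will be applied, three different flows will be utilized at a random sequence: 20, 40, and 60 L/min". Data Collection describes monitoring at the three flows on both devices. Nothing allocates volunteers to a device, and no sentence says that each volunteer uses both.

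**The concern.** If the same 26 people use both devices, the two sets of device readings are paired. A Mann-Whitney or independent t test leaves the person-to-person variation in its error term, although that variation cancels when each person is compared with themselves. With positive within-person correlation, the stated standard error is too large. Confidence intervals are then too wide, and a real device difference is more likely to be reported as no difference.

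There is a second gap. Because the unit of analysis is not stated, an analyst could stack the three flows as 78 rows per device. The rows would then be neither independent between devices nor independent within a device.

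**Working it through.** **1. Which design do the documents describe?** One cohort, one group, two devices applied and no allocation all point to both devices per person. The crossover and single-group labels fit this, but the flows alone would satisfy both. The session length in Study Procedure gives a rough check (5 min mask baseline, 20 min room air, 20 min per flow, 5 min break between flows):

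- Two devices: 5 + 20 + 6×20 + 5×5 = 170 min, 10 min under 3 hours.
- One device: 5 + 20 + 3×20 + 2×5 = 95 min, 85 min under 3 hours.

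The stated length is 3-4 hours. The two-device total assumes a 5-minute break at the device switch; without it the total is 165 min. Adding the 30-minute consideration period in step 3 brings one device only to 125 min, still 55 min short. The timing supports two devices per person without proving it.

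**2. One value per person per device (for example, at one flow).** The plan gives no power figure for the device comparison, so there is none to reproduce. The 26 was sized on a flow contrast. The documents give no within-person correlation r, device effect or SD, so r is an assumed range and the device difference is expressed in outcome SDs.

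- True variance of the mean device difference: 2σ²(1−r)/26.
- Variance assumed by the independent t test: 2σ²/26.
- Standard error too large by 1/√(1−r).
- 95% interval wider than the paired one by (2.009/2.060)/√(1−r) = 0.975/√(1−r), using t quantiles on 50 and 25 degrees of freedom.

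Simulation with normal data, two-sided 5%, 200,000 runs per r, and the device difference held at 0.572 outcome SD (the value at which the paired test has 80% power at r = 0.5):

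| r | Type I error, independent t | Interval width ratio | Power, independent t | Power, paired t |
|---|---|---|---|---|
| 0.1 | 4% | 1.03 | 53% | 55% |
| 0.2 | 3% | 1.09 | 53% | 60% |
| 0.3 | 2% | 1.17 | 53% | 66% |
| 0.5 | 0.7% | 1.38 | 54% | 80% |
| 0.7 | 0.1% | 1.78 | 55% | 95% |

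The paired t test's type I error is 5% throughout. The rank tests behave alike: at r = 0.5 and the same effect, Mann-Whitney has about 50% power against 78% for Wilcoxon signed-rank. Below r of about 0.05 pairing gains nothing; at r = 0 it costs 1-2 points of power.

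**3. Three flows stacked as 78 against 78 rows.** Write Vp, Vpd and Ve for the person, person-by-device and error variances (assumed, no flow effect).

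- Independent test: true over assumed variance of the device difference = (3Vpd + Ve)/(Vp + Vpd + Ve), above 1 when Vpd > Vp/2.
- Paired test on 78 row pairs: true over assumed variance = (3Vpd + Ve)/(Vpd + Ve), above 1 whenever Vpd > 0.

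| Vp / Vpd / Ve | Variance ratio, independent | Type I error, independent on rows | Type I error, paired on rows | Type I error, paired on three-flow means |
|---|---|---|---|---|
| 0.5 / 0 / 0.5 | 0.5 | 0.7% | 5% | 5% |
| 0.5 / 0.1 / 0.4 | 0.7 | 2% | 10% | 5% |
| 0.4 / 0.2 / 0.4 | 1.0 | 5% | 13% | 5% |
| 0.3 / 0.3 / 0.4 | 1.3 | 9% | 15% | 5% |

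Stacking can therefore err either way under the plan's test, and pairing the stacked rows does not cure it.

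**4. Testing at each flow.** Each per-flow paired test holds 5%, but there are three per outcome. Under the same four variance sets, the chance of at least one false positive for one outcome is 13-14%.

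**The case against.** The strongest objection is that both devices per person is an inference. Step 8 joins the two devices' flow readings with the word *or*, which fits one device per volunteer. Step 6 describes three flows rather than six periods and mentions no device switch. The choice of an independent-groups test may itself show what was intended. These points stand as weak evidence. They do not outweigh the absence of any allocation and the poor fit of 95 minutes to 3-4 hours. If separate groups were meant, the allocation is missing, and an equal split would leave 26/2 = 13 people for each per-device flow analysis. Steps 6 and 8 and the Data Analysis section need reconciling on either reading.

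The second objection is that the consequence is limited: the outcome is secondary, the per-flow error is conservative, r is unknown, and the loss is small at r of 0.2 or below (at most 7 points of power in the table above). That is all correct, and it caps the importance of the point.

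Two stronger readings should be resisted. A reader might infer that correlation itself drags the planned test's power down, to about 25% at r = 0.7. That figure arises only if the effect is fixed at 0.572 SD of the paired differences, so that the raw device difference shrinks from 0.77 to 0.44 outcome SD as r goes from 0.1 to 0.7. At a fixed raw difference the planned test's power is flat, and what is lost is the gain from pairing. A reader might also infer that the plan inflates false positives. That could happen only if flows were stacked and person-by-device variance exceeded half the person variance, and the plan does not say that flows will be stacked.

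**Conclusion.** The point holds, conditional on each volunteer using both devices, which the documents imply but do not state. On that reading the named device tests do not match the design. Compared per flow, with 26 people and r of 0.3 to 0.7, they forgo about 13 to 40 points of power (66 − 53 and 95 − 55) at a difference of 0.572 outcome SD, and widen the interval by a factor of 1.17 to 1.78. At r of 0.2 or below the cost is small. These sizes rest on normal data and on assumed values of r and of the device difference. They illustrate the loss and do not predict this trial's power.

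A reader might go on to infer that the primary result is compromised. On the two-device reading it is not, because flows are already analysed within subject. The correction should be made, but it concerns a secondary outcome.

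**What to change.** Replace the device sentence in Data Analysis with a within-subject comparison, for example:

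> For each outcome, each subject's mean over the three flows will be compared between devices with a paired t test, or a Wilcoxon signed-rank test if the paired differences are not normal. Paired comparisons at each flow are supportive.

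This gives one main device test per outcome and avoids three competing ones. An alternative is a mixed model with device, flow and device-by-flow effects and random subject and subject-by-device effects. Flow rows should not be stacked and treated as independent values or as independent pairs.

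In step 6, state whether each subject uses both devices and, if so, that device order is randomised. The present text randomises only the flows, and a fixed device order would confound device with time. If separate device groups are intended, keep the named tests and state in Methods and Study Procedure how people are allocated and how many use each device.

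The cost is one sentence in each of two sections, with no extra volunteers, visits or measurements. The test can be changed at any time before analysis; device order should be settled before enrolment.

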## **Data Collection:**

All the following data will be collected from the participant and/or during the study.

**Demographic variables:** Age, sex, and ethnicity

**Anthropometric variables:** Height, weight

**Study variables:** Baseline PTIF, respiratory rate and tidal volume via NICO2 (Respironics, Murrysville, PA, USA). Continuous monitoring of PTIF, and respiratory rate during 3 different flow settings via two HFNC devices. Comfort level reported by participants using a visual numerical scale ranging between 0 (extreme discomfort) and 10 (very comfortable) at the end of each flow setting. Quantifying aeration homogeneity using electronic impedance tomography device by assessing EELI, regions of interest (ROI1, ROI2, ROI3, ROI4), and center of ventilation (CoV) during the 3 different flow settings.

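### Mask and HFT7500 PTIF are compared only by correlation, which cannot show how far the two readings differ in L/min

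*Combined protocol and SAP*

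**What the plan says.** All references are to the combined protocol and SAP.

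- **Introduction.** It states that "the accuracy and effectiveness of these devices remain unknown" and gives this as the reason to measure PTIF by mask and to "compare the flows with those displayed by the HFNC devices during treatment, particularly at different flow settings". It also suggests that continuous PTIF could help clinicians choose and adjust the flow for different patients.
- **Abstract.** The secondary outcome is worded as a correlation between the subject's "peak inspiratory flow measured by HFNC and by a mask connected with a respiratory monitor".
- **Outcomes.** Mask PTIF is set beside HFT7500 PTIF, and beside the Airvo 3 waveform, at three flow settings. No measure of agreement is named.
- **Data Analysis.** Spearman's rho is allowed, or else "Pearson Correlation statistical test will be used to assess the correlation between PTIF measured via mask (NICO2) with PTIF measured by the" (here, the HFT7500). No method is named for mask against Airvo 3. Separately, Friedman or repeated-measures ANOVA compares baseline with the three flows for each device, and PTIF is among the continuous variables to be summarised.
- **Study Procedure, steps 5 to 7.** The mask is used at baseline and then as follows: "Between flow settings, PTIF will be measured via the mask and respiratory monitor". During those intervals, "HFNC will be removed during the break".
- **Data Collection.** For the mask, it lists "Baseline PTIF, respiratory rate and tidal volume via NICO2". The later mask readings of step 7 are not listed.

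**The concern.** Whether a displayed flow is accurate is a question about differences in L/min: how far the device reads from the mask on average, and how widely that difference varies between people. A correlation answers neither part. It measures how closely the two readings follow a straight line (Pearson) or a common ranking (Spearman), and it is unchanged if every device value is shifted by the same amount.

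Followed as written, the plan would report r with a p-value, summaries of PTIF, and a test of baseline against flow settings. A reader who wants to know how far one person's HFT7500 reading may lie from the mask reading at 20, 40 or 60 L/min would not find it. That is the figure needed for the individual use that the Introduction has in mind.

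Airvo 3 has a further gap. The Introduction says that it "provides a continuous waveform reading of the targeted flow", while Outcomes calls the signal a PTIF waveform. Nowhere is the number named that is to be set against mask PTIF.

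**Working it through.** The plan gives no figure for PTIF correlation or agreement, so there is none to reproduce. The 26 subjects come from an EELI calculation that is not at issue here. The documents give no PTIF standard deviations, so the L/min values below are assumptions.

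**1. Offset.** Let mask PTIF have SD s, and let device = mask + b + d, where b is the mean difference and d varies independently of the mask reading with SD e. Then r = s / sqrt(s^2 + e^2), and the 95% limits of agreement are b +/- 1.96e. The offset b does not enter r.

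| s | e | b | r | Limits (L/min) |
|---|---|---|---|---|
| 8 | 3 | 0 | 8/sqrt(73) = 0.94 | -5.9 to +5.9 |
| 8 | 3 | -10 | 0.94 | -15.9 to -4.1 |
| 5 | 3 | 0 | 5/sqrt(34) = 0.86 | -5.9 to +5.9 |
| 8 | 4.8 | 0 | 8/sqrt(87.04) = 0.86 | -9.4 to +9.4 |
| 8 | 9 | 0 | 8/sqrt(145) = 0.66 | -17.6 to +17.6 |

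Rows 1 and 2 show that r misses the shift. Rows 3 and 4 show that r does not fix the limits either.

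**2. The p-value.** With n = 26, a Pearson r is significant at 0.05 (two-sided) from t/sqrt(24 + t^2), with t the 97.5% point on 24 df, which is about 0.39. Every r in the table exceeds this, so a significant correlation says little about accuracy.

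**3. What b and e contain.** The mask is read with HFNC off and the device with HFNC on. A perfect device, with a real on/off change in PTIF of mean -10 and SD 3 L/min, gives exactly row 2. The table therefore describes device-minus-mask differences, not device error alone.

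**4. Could the ANOVA fill the gap?** If baseline PTIF is the mask value and on-flow PTIF the device value, it could show a mean shift. A difference of 10 L/min gives a paired t of 10/(3/sqrt(26)) = 17.0 at e = 3 and 10/(9/sqrt(26)) = 5.7 at e = 9. In 20,000 simulated trials (n = 26, s = 8, mask baseline plus three device readings, no sphericity correction), that shift was significant in 100% at either e. With b = 0, p < 0.05 occurred in about 6% at either e, although the limits are +/-5.9 in one case and +/-17.6 L/min in the other. The test cannot see the spread.

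**5. Could a reader rebuild the limits?** The SD of the differences is sqrt(s1^2 + s2^2 - 2 r s1 s2). With s1 = 8, s2 = sqrt(73) = 8.54 and r = 8/sqrt(73), this is sqrt(64 + 73 - 128) = 3.0. It needs means, SDs and Pearson r for the same pairs at each flow. Data Analysis allows medians and Spearman instead, and does not say that the correlation is computed per flow.

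**6. Precision of the alternative.** With 26 pairs at a flow (assuming that all 26 subjects use the HFT7500), the 95% CI half-width is t(25)/sqrt(26) = 0.40 SD of the differences for the mean difference, and about t(25) x sqrt(3/26) = 0.70 SD for each limit. If that SD is 3 L/min, these are 1.2 and 2.1 L/min; if it is 9, they are 3.6 and 6.3 L/min.

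**The case against.** The strongest reply is that the plan is consistent with its declared outcome: the Abstract promises a correlation and Data Analysis delivers one. The stated aim and hypothesis concern lung aeration, and no section lists device validation as an endpoint. This stands in part and lowers the weight of the point. It does not remove it, because the Introduction presents the mask comparison as the response to unknown accuracy, and Outcomes does not limit the comparison to correlation.

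A second reply is that limits of agreement would not settle accuracy either, since mask and device are not read under the same conditions. That is correct, and the report should say so. But the same timing affects the correlation, and a difference in L/min with this caveat tells the reader more than r does.

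A third reply is that the paired readings will exist, so agreement could be computed later. True, but a choice made after the data are seen leaves room to pick the more flattering statistic.

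Three stronger readings are tempting, and the documents do not support them:

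- *Nothing in the plan could reveal a bias.* The baseline-versus-flow test could show a mean shift. It is not presented as a device comparison, mixes measurement method with flow effect, and gives no limits.
- *Correlation hides any proportional error.* That holds only for pure rescaling, where the scatter shrinks with the reading. For a device reading 30% low (assumed mask mean 35) with scatter held at 3 L/min, r falls to 5.6/sqrt(31.36 + 9) = 0.88. The mean difference is -10.5 and the limits are -10.5 +/- 1.96 x sqrt(0.09 x 64 + 9), that is -18.0 to -3.0.
- *The differences would measure device error.* Step 3 of the working shows why they cannot.

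**Conclusion.** The concern holds for the mask-versus-device PTIF comparison. The only method named, a correlation for the HFT7500, cannot show a constant offset. In the example, an r of 0.94 is compatible with a mean difference of 0 or of -10 L/min. That example rests on an assumed mask SD of 8 and an assumed SD of differences of 3 L/min; that r does not depend on the offset holds whatever the SDs. The differences include any real change in PTIF on HFNC.

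The point should be fixed but is limited in reach. It concerns a secondary outcome in a small volunteer study. A reader might infer that the main result is weakened; it is not, since the primary outcome (lung aeration) and the sample size do not depend on this analysis.

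**What to change.** - **HFT7500.** Add a Bland-Altman analysis at each of 20, 40 and 60 L/min: mean difference (device minus mask, L/min) and 95% limits of agreement, each with a 95% CI. Do not report limits pooled across flows unless flow is modelled and repeated pairs within a subject are allowed for; otherwise any real flow effect enters the limits.
- **Correlation.** Keep it as descriptive, with one coefficient per flow.
- **Prespecify** the averaging window for the continuous device reading, and which mask reading each device value is paired with.
- **Wording.** Change the Abstract's secondary outcome from correlation to agreement. Add the mask readings of Study Procedure step 7 to Data Collection. State that mask PTIF is taken with HFNC off, so the difference cannot isolate device error.
- **Airvo 3.** Name the number to be compared with mask PTIF, or call that outcome descriptive.

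The readings are already planned in Study Procedure steps 5, 7 and 8, so no new measurement is needed. The cost is a little more analysis work, small edits to the Abstract and Data Collection as well as Data Analysis, and a result that may look less favourable than a high r.

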## **Outcomes**

- Lung aeration, EELI, respiratory rate, and comfortable level compared at baseline (without HFNC device) with 3 different flow settings
- Lung aeration, EELI, respiratory rate, and comfortable level between two HFNC devices (Airvo 3 vs HFT7500)
- PTIFs measured by the mask with respiratory monitor and by the HFT7500 device during the HFNC treatment at three flow settings.
- PTIFs measured by the mask with respiratory monitor and PTIF waveform monitored by the Airvo 3 device during the HFNC treatment at three flow settings.

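### The mask-versus-HFT7500 PTIF correlation takes no account of repeated readings per person: pooled, its p-value is too small; run per setting, it does not assess within-person tracking

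*Combined protocol and SAP*

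**What the plan says.** The Methods section describes a "Randomized crossover trial". Under Study Procedure, "three different flows will be utilized at a random sequence: 20, 40, and 60 L/min". The same list adds: "Between flow settings, PTIF will be measured via the mask and respiratory monitor", and on the breaks: "There is a 5 min break between flows. HFNC will be removed during the break". The Outcomes section sets the comparison as "PTIFs measured by the mask with respiratory monitor and by the HFT7500 device during the HFNC treatment at three flow settings".

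For this outcome the Data Analysis section gives a single sentence, which names Spearman's rho, or else: "Pearson Correlation statistical test will be used to assess the correlation between PTIF measured via mask (NICO2) with PTIF measured by" (device: HFT7500), with significance at p < 0.05. It does not say whether the three settings are pooled, averaged within a person or analysed one at a time. It plans no confidence interval for the correlation. Repeated-measures methods (Friedman or repeated-measures ANOVA) are named in the same section, but only for comparing baseline and flow settings.

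The Introduction motivates the work by saying that continuous PTIF monitoring "could serve as an objective reference for practitioners when determining the initial flow and flow titration". It also describes the mask measurement as taken before HFNC is applied, whereas Study Procedure has further mask readings between flows.

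**The concern.** An ordinary Pearson or Spearman test assumes that the pairs are independent. Here one person can contribute several pairs. Two consequences follow, depending on how the unqualified sentence is carried out.

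- **Settings pooled.** Each person is counted up to three times, so the p-value is too small. Any interval computed from the same pairs would be too narrow.
- **Settings analysed separately.** Each p-value is valid, but the analysis only asks whether people with high mask PTIF also read high on the device. It does not ask whether the device follows a change within one person.

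The second question matters because the Introduction mentions titration, which concerns change within a person, as well as the choice of initial flow, which is largely a between-person matter. This correlation is the only analysis the plan names for the HFT7500 readout against the mask, so readers are likely to use it for both purposes.

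**Working it through.** **Inputs from the documents.** 26 persons ("the sample size is calculated to be 26"); three flow settings; significance level 0.05, taken as two-sided because the plan does not say. The 26 was derived for EELI. The plan gives no expected correlation, interval or power for PTIF, so there is no figure of its own to reproduce here.

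**Inputs assumed.** Every person uses the HFT7500 at all three settings, with one mask reading paired to each, giving 26 × 3 = 78 pairs. Repeatability (the correlation between two readings of the same person on the same instrument, ρ) is 0.5 to 0.9; the documents give no value. Readings are normal, with no systematic shift between settings.

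**Step 1: pooled test when there is no association.** The variance of the pooled correlation is inflated by about D = 1 + (3 − 1) × ρ(mask) × ρ(device). The effective number of pairs is 78 / D. The nominal 5% test then rejects with probability of about 2 × [1 − Φ(1.96 / √D)]. A simulation of 8,000 trials per row, with no true association, checks this.

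| ρ mask, ρ device | D | 78 / D | Rejects, formula | Rejects, simulated | Coverage of nominal 95% interval, simulated |
|---|---|---|---|---|---|
| 0.5, 0.5 | 1.50 | 52.0 | 11% | 11% | 89% |
| 0.7, 0.7 | 1.98 | 39.4 | 16% | 17% | 83% |
| 0.8, 0.8 | 2.28 | 34.2 | 19% | 20% | 80% |
| 0.9, 0.9 | 2.62 | 29.8 | 23% | 24% | 76% |
| 0.8, 0.1 | 1.16 | 67.2 | 7% | 7% | 93% |

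The last row shows that the problem is small if either instrument is only weakly clustered. A repeat simulation of that case gave about 6%.

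**Step 2: width of an interval, if one were reported.** The Fisher-z standard error is 1/√(78 − 3) = 0.115 for 78 independent pairs and 1/√(26 − 3) = 0.209 for 26. At an illustrative r of 0.72 the 95% intervals are 0.59 to 0.81 and 0.46 to 0.87.

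**Step 3: what the correlation measures.** With equal repeatability on both instruments, expected r = ρ × r(between) + (1 − ρ) × r(within). With assumed ρ = 0.8, r(between) = 0.8 and r(within) = 0:

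0.8 × 0.8 + 0.2 × 0 = 0.64.

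The same value is expected for a correlation run at a single setting, because one reading per person has the same variances and covariance. In simulation the pooled version was significant in over 99% of trials, while the within-person correlation averaged 0.00. With r(between) = 0.9 and ρ from 0.5 to 0.9, the simulated pooled r ran from 0.44 to 0.80, again with a within-person correlation of 0.00.

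**Step 4: which pairs exist.** Three flows on one device leave only two gaps between them. If the mask value is a single reading before HFNC, as the Introduction describes, then ρ(mask) = 1 and D = 1 + 2 × ρ(device). That is 2.0 at ρ(device) = 0.5 and 2.8 at 0.9, so pooling is still wrong, and a within-person correlation cannot be computed at all. If three separate mask readings can be paired, a repeated-measures correlation has 26 × (3 − 1) − 1 = 51 degrees of freedom.

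**The case against.** The strongest reply is that pooling is nowhere stated. The Outcomes wording fits three per-setting correlations with 26 pairs each just as well, and the same Data Analysis section handles the three settings as repeated measures elsewhere. That stands. A reader might infer that a flawed pooled test is planned, but the documents support only the statement that the unit of analysis is left open. Nor is a confidence interval planned, so the direct effect of pooling would be on the p-value.

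Two further points stand in part. The size of the error depends on repeatability values that the documents do not give, and it can be slight, as the last row of the table shows. The null of no association is also of limited interest for two instruments measuring the same person's inspiratory flow.

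A stronger reading is that a within-person correlation near zero would show that the device does not follow the person. The documents do not support this. The mask is read during breaks with HFNC removed and the device is read on therapy. In resting volunteers whose effort is not deliberately varied, an accurate device could give a low within-person value simply because fluctuations on therapy do not persist into the break.

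Finally, the Introduction's remark on titration is background and is joined to the choice of initial flow, a question that a between-person correlation does address. No titration claim is listed among the outcomes. The concern is therefore about what the result may be used to support, not about a claim the plan already makes.

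**Conclusion.** The point holds in conditional form. The named method ignores repeated readings, and the plan does not say how they will be handled. If the settings are pooled as independent pairs, the nominal 5% test has a false-positive rate of about 11% to 24% under repeatability of 0.5 to 0.9 on both instruments, and about 6% to 7% if one instrument is weakly clustered. If they are analysed separately, the p-values are valid. On either reading, within-person tracking is not assessed, and a correlation of about 0.64 can arise entirely from person-to-person differences under the stated assumptions.

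These figures rest on assumed repeatability and on 78 available pairs, which the documents do not confirm. The calculations do not show that the HFT7500 fails to track, nor that pooling is intended. The point concerns the HFT7500 only; the Data Analysis section names no correlation for the Airvo 3 waveform. It affects a secondary outcome and leaves the primary EELI outcome untouched.

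**What to change.** Amend the Data Analysis section as follows.

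1. State that the three settings will not be pooled as independent pairs.
2. State which mask reading is paired with each device setting, reconciling the Introduction (mask before HFNC) with Study Procedure (mask between flows).
3. Report the correlation at each setting (n = 26 each, if all persons use the HFT7500), or of person means, and label it as the between-person result.
4. Where repeated mask readings exist, add a repeated-measures correlation, or a mixed model of device PTIF on within-person-centred mask PTIF, with intervals obtained by resampling participants.
5. State that a between-person or pooled correlation will not be used to support a statement about within-person tracking or titration. Report the within-person result with the caveat that mask and device readings are not simultaneous, so a low value does not by itself show device failure.

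The cost is analysis wording plus a pairing rule; no extra measurements are needed beyond those in Study Procedure. Intervals will be wider than from pooled pairs, and the within-person estimate will be imprecise with so few readings per person. If only one mask reading per person proves usable, item 4 drops out, and the report should say that within-person tracking was not assessed.
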